### Baseline Analysis and descriptive statistics

Equivalence of participants in the intervention and control arms will be assessed on demographic and clinical variables, including outcomes, health status, co-morbidity, and utilization variables. Because this is a randomized controlled trial, no systematic bias is anticipated. However, we will conduct adjusted analyses and use as covariates those factors that are thought *a priori* to be related to the primary and secondary outcomes. We will report summary statistics for all baseline covariates and outcomes (means, standard deviations, and quartiles for continuous variables; frequencies and percentages for binary variables) by randomized group.

### Primary Effectiveness Analyses for Specific Aims 1 & 2

Since there are multiple patients enrolled per physician and multiple patients enrolled per peer health coach, a physician-level and peer health coach random effect will be included in the

primary analytic model to take this correlation into account. For the Aim 1 primary outcome analysis, we will evaluate change in systolic blood pressure, from baseline to 12 months, in the intervention versus controls using the following random effects model:

$$Y_{ij} = \mu + \beta_1 Group_{ij} + \beta_2 Baseline_{ij} + \beta_3 x_{ij} + \alpha_j + Group_{ij} * \tau_k + \epsilon_{ijk}$$

where  $Y_{ij}$  is the change in blood pressure from baseline to 12 months for subject  $i$  having provider  $j$  (and  $k$  for peer coach intervention participants);  $\mu$  is the overall mean;  $Group_{ij}$  is group assignment (intervention vs. control);  $Baseline_{ij}$  is the baseline BP value;  $x_{ij}$  are baseline covariates that could affect the outcome as outlined in Section C.6.5;  $\alpha_j$  is the random effect for provider cluster  $j$  and  $\tau_k$  is the random effect for peer coach cluster  $k$  (note that  $\tau_k$  is multiplied by the intervention indicator  $Group_{ij}$  so that the added peer coach correlation is accounted for only amongst intervention participants, as suggest by Roberts et al). Our main goal is to test whether  $\beta_1 = 0$  which is the difference in BP change (from baseline to 12 months) between the intervention and control groups. All Aim 1 secondary outcomes and Aim 2 intermediate outcomes will be compared between intervention and control participants using the same model above for continuous outcomes and using a logit link for the same model for binary outcomes. We will include a sensitivity analysis that will explore whether intervention fidelity influences the effect of the intervention on primary outcomes, treatment receipt ("dose" of intervention: number of visits, phone calls, proportion of required modules delivered).

### Specific Aim 3

We will calculate intervention costs per patient. These costs will include all labor and materials (pamphlets, home BP monitors, etc.) used in the intervention divided by the number of participants.

### Specific Aim 4 - Qualitative analysis

Transcripts will be analyzed using simultaneous deductive and inductive content analysis. Inductive content analysis consists of open/unstructured coding and allows for the identification of emergent previously unidentified or unexpected themes while deductive content analysis is more structured and consists of identifying meaning units that fit within pre-identified a-priori categories. A-priori codes for patient interviews will include, but not be limited to: patient satisfaction, barriers and facilitators to participation, and acceptability. A-priori codes for staff interviews will include, but not be limited to: barriers and facilitators to implementation, and sustainability acceptability, and changes in PACT team involvement in care. Coding will be done while simultaneously listening to the audio file and reading the transcripts. Sub-codes will be developed by identifying broad themes followed by sub-coding schemes based on representative recordings. Quotes that do not accurately fit existing sub-codes will be used to develop new sub-codes iteratively. Qualitative data collection and analysis will be blind regarding participants' responder/non-responder status until the final merging stage of analysis. The results of the analysis process will be reviewed by members of the research team to assess their thoroughness and comprehensiveness for analytical rigor. Accountability will be supported by confirming results with respondents in subsequent interviews.

### Missing data analyses

All appropriate efforts will be made to avoid missing data. Accruing data will be monitored for the presence of missing values, and the study coordinator will investigate causes and/or remedies for missing data. For key analysis variables that have 15% or more missing values, we will analyze patient and clinical factors that are associated with having a missing value. We will then perform analyses using multiple imputations to impute these key variables to allow

analysis for all subjects and reduce any bias associated with the missing data. We will perform a sensitivity analysis to determine if missing values have an effect on study outcomes.

### **Study power and sample size**

We have powered our study to detect a clinically significant change in systolic blood pressure (SBP) of 5 mmHg) consistent with findings from other peer support and CHW studies. The sample size we project is n= 354 Veterans, which assumes 80% power, 15% attrition, alpha 0.05, a PEER ICC 0.007, a provider ICC 0.015, provider cluster size of 5 (70 providers), PEER cluster size of 35 (5 PEER coaches). The SD of 14.2 mmHg was taken from a recently published review of CV risk factors among Veterans. We estimate we will lose 15% of the sample (n=53), which would result in a final sample size of N=400(or 200in each arm), similar to our rate in our ongoing CHW trial and previous CHW studies. Because of the potential for multiple patients enrolled per physician, we have adjusted both sample size calculations for potential clustering by physicians within the clinic, using estimates of ICC = 0.015 based on other published hypertension trials among primary care practices and clustering by Veteran peer health coach ICC = 0.007, based on a randomized trial of peer support among individuals with diabetes. We will randomize n=200 Veterans to the control and n=200 Veterans to the intervention group (which will ultimately be reduced to 177 Veterans in the control and 177 Veterans in the intervention group after an estimated 15% loss of participants), to have a power of 80% to detect a difference of 5 mmHg in systolic blood pressure between groups.

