### Study design overview:

We propose a randomized controlled trial to evaluate the effectiveness of **Vet-COACH**, a peer health coach program to control hypertension and reduce CVD risk among Veterans. The original program incorporated home visits by peer health coaches to deliver health education, counseling and goal setting support. Due to safety concerns and social distancing restrictions stemming from the COVID 19 pandemic, the program has transitioned to conducting all health coaching encounters, as well as enrollment and exit visits, via phone. This transition was implemented under IRB approval of the miscellaneous memo submitted at the beginning of the pandemic. These changes to conduct all health coaching encounters and exit surveys over the phone will be permanent for the remainder of the study. Our operations partners from NCP have developed extensive patient educational materials that will be used for the current study. We will train the peer health coaches to provide brief educational messages and link Veterans to existing clinical services at VHA, including their primary care PACT teams and community based programs. The main outcome will be a reduction in systolic blood pressure. Secondary outcomes are cardiovascular risk, as measured by the Framingham Risk Score (FRS), health care utilization and intermediate behavioral outcomes including patient activation, social support and health behaviors (e.g. diet and physical activity, medication adherence). *We will randomize a total of 200 individuals to the intervention group and 200 individuals to the control group.*

Our study design has limitations. Because of the nature of the intervention, we are unable to blind treatment assignment. The PI and [name] will provide overall supervision to the peer coaches. This model is necessary for program development. Because the intervention is being conducted at two sites, we are not proposing an economic evaluation to estimate cost-effectiveness, in part because such data would be of limited generalizability. Positive findings will lead to a larger multi-site trial that would include a cost-effectiveness analysis. These limitations are more than balanced by the strengths of this proposal. The proposed project is a prospective, randomized controlled trial that examines important outcomes with statistical power to detect clinically meaningful differences.

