## 5.2 Recruitment Methods

- State how many subjects will be needed.
- Describe when, where, how and by whom potential subjects will be identified and recruited.
- Describe materials that will be used to recruit subjects, e.g., advertisements. Include materials as an appendix or separate attachment. Only refer to attachments as A, B, etc. Do not refer to version #'s or dates of versions. During the course of the study, changes in the attachments will require IRB approval; however, those changes may not require a revised protocol.
- Describe any payments to subjects, including the amount, timing (at the end of the study or pro-rated for partial study participation), method (e.g., cash, check, gift card), and whether subjects will experience a delay in receiving the payment.

Eligibility for participation will be determined by identification of potential participants and Vet-Coachers from VA administrative data files from VA Corporate Data Warehouse, as well as the "Quality Improvement for Primary Care Clinic" project conducted through the Seattle VA Primary Care Clinic for relevant diagnostic and lab-based criteria. Census tract data from the Quality Improvement project will be linked to subject geographic data (address) in the VA administrative files. This information will be obtained by the project programmer. Using administrative data, we identified approximately 17,080 Veterans at VA Puget Sound (cared for at either the Seattle or American Lake Divisions) with hypertension, of whom n=2,955 have a systolic blood pressure that is > 150 mm Hg. Approximately 90% of this population is overweight or obese (a second criteria for entry into the study) (n=2,486). Our target sample size for recruitment is n=400. A letter from the study signed by the primary care provider (PCP) with an opt-out option will be

mailed to potential participants informing them of the project and encouraging participation. Project staff (project manager and research assistant) will then contact patients by telephone to assess eligibility and interest in participation and to arrange an enrollment visit.

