All Aim 1 secondary outcomes and Aim 2 intermediate outcomes will be compared between intervention and control participants using the same model above for continuous outcomes and using a logit link for the same model for binary outcomes.

Sensitivity analyses

We will include a sensitivity analysis that will explore whether intervention fidelity influences the effect of the intervention on primary outcomes, treatment receipt (“dose” of intervention: number of visits, phone calls, proportion of required modules delivered). This approach will allow for testing whether greater participation in the intervention was associated with a greater impact on SBP, and if that impact was different for those with different SBP at baseline (include baseline blood pressure in the primary analysis). We will also add a sensitivity analysis among patients enrolled after the COVID pandemic, when all study activities were moved to remote/virtual.

Exploratory Analysis:

1. Restrict sample was restricted to patients who met criteria for uncontrolled hypertension (BP \geq 140/90 mmHg)
2. Pre- vs. During pandemic
 - a. Demographics of Veterans enrolled post-COVID versus pre-COVID – are the Veterans enrolled post-COVID different than Veterans enrolled pre-COVID?
 - b. Separate analysis of primary/secondary outcomes for (1) Veterans with 12 month outcome collected pre-COVID and (2) Veterans with 12 month outcome collected post-COVID – are treatment effects different post-COVID?
3. Secondary analyses to adjust for important baseline covariates in our models. Prespecified variables age, race [others to consider diabetes status because there is a different goal blood pressure for patients with diabetes]

Missing data analyses

If outcome is missing (e.g. exit blood pressure) then will use value in CPRS on the date closest to the exit date (must be +/- 3 months around the date of the exit visit).

- Use outpatient blood pressure as defined by EPRP (EPRP documentation in Teams)

For key analysis variables that have 15% or more missing values, we will analyze patient and clinical factors that are associated with having a missing value. We will then perform analyses using multiple imputations to impute these key variables to allow analysis for all subjects and reduce any bias associated with the missing data. We will perform a sensitivity analysis to determine if missing values have an effect on study outcomes.

Baseline Analysis and descriptive statistics

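### A 15% loss from 200 per arm leaves 170, not 177, and the sample size paragraph uses 354 both as the N that allows for attrition and as the N left after it

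*Protocol*

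**What the plan says.** Protocol section 5.6, Study power and sample size, holds the only sample size justification in either document. In order, it makes these statements:

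- The projected size: "The sample size we project is n= 354 Veterans, which assumes 80% power, 15% attrition". The inputs are a 5 mmHg difference, SD 14.2 mmHg, alpha 0.05, a provider ICC of 0.015 with clusters of 5, and a peer coach ICC of 0.007 with clusters of 35 (5 coaches).
- The loss and the final number: "We estimate we will lose 15% of the sample (n=53), which would result in a final sample size of N=400", given as 200 per arm.
- The number left from 200 per arm: "which will ultimately be reduced to 177 Veterans in the control and 177 Veterans in the intervention group after an estimated 15% loss".
- The power attached to those 177 per arm: "to have a power of 80% to detect a difference of 5 mmHg in systolic blood pressure between groups".

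The number to randomise is the same elsewhere in the Protocol. The Study design overview says: "We will randomize a total of 200 individuals to the intervention group and 200 individuals to the control group". Section 5.2 says: "Our target sample size for recruitment is n=400".

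Two further passages bear on the check. The primary model puts in a coach random effect "so that the added peer coach correlation is accounted for only amongst intervention participants" (Protocol 5.6, Primary Effectiveness Analyses). The SAP, section 6, Missing data analyses, adds a fallback for the endpoint: "If outcome is missing (e.g. exit blood pressure) then will use value in CPRS on the date closest to the exit date", within 3 months either side of the exit visit.

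**The concern.** Four statements are made together: 400 randomised, 15% loss, 177 completers per arm and 80% power. The first three cannot all be true, because 15% of 200 is 30, not 23.

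The second fault is that 354 changes role within the paragraph. It starts as a number that already allows for attrition, and the stated loss of 53 is 15% of it. It ends as the number left once attrition has happened.

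This decides what 400 means. If 354 is the number to randomise, 400 contains a margin. If 354 is the number of completers needed, 400 is short at 15% loss. A reader cannot tell which. Anyone taking planned completers and planned power from this paragraph gets a count that is 14 too high, and a power figure whose basis cannot be identified.

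**Working it through.** **Attrition arithmetic** (Protocol figures only)

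- 200 × (1 − 0.15) = 170 per arm; 400 × 0.85 = 340 in total.
- Loss implied by 177: (200 − 177)/200 = 11.5%.
- 0.15 × 354 = 53.1, so the stated loss of 53 is 15% of 354, not of 400 (which would be 60).
- Routes from 354 to 400: 354 + 53 = 407; 354/0.85 = 416.5. Neither gives 400. Backwards, 400 − 53 = 347, not 354.

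**Inputs for sample size and power.** Difference 5, SD 14.2, alpha 0.05, 80% power, ICCs and cluster sizes: Protocol 5.6. Two-sided test: SAP section 6. Coach clustering in the intervention arm only: the Protocol's primary model.

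- Unclustered n per arm = 2 × [14.2 × (1.960 + 0.842)/5]² = 126.6; total 253.2.
- Provider design effect = 1 + 4 × 0.015 = 1.06.
- Coach design effect = 1 + 34 × 0.007 = 1.238.

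**Can 354 be reproduced?**

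1. *Large-sample, coach clustering in the intervention arm only.* Mean design effect 1.06 × (1 + 1.238)/2 = 1.186. Completers 253.2 × 1.186 = 300.4. Randomised 300.4/0.85 = 353.4. This gives 354 as the **number to randomise**; 354 × 0.85 = 300.9 completers.
2. *Large-sample, both design effects in both arms.* 1.06 × 1.238 = 1.312. Completers 332.3; randomised 390.9. This gives 354 in neither role.
3. *Satterthwaite degrees of freedom, coach clustering in the intervention arm only.* The intervention-arm variance has 5 − 1 = 4 df and the control-arm variance n − 1; power comes from the noncentral t. The combined df is about 12.9. Power is just under 80% at 176 per arm and 80.1–80.2% at 177. This gives 354 as the **completers needed**, with 354/0.85, about 417, to randomise.

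Both roles can therefore be reached from the stated inputs, and the paragraph does not say which calculation was done.

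**Power at 5 mmHg.** Large-sample formula: Φ(5/SE − 1.960). With one-arm coach clustering, SE = 14.2 × √[1.06 × (1 + 1.238)/n], which is 1.677 at n = 170. With both effects in both arms, SE = 14.2 × √[1.06 × 2 × 1.238/n], which is 1.764 at n = 170.

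| Method | 170 per arm | 177 per arm |
|---|---|---|
| Large-sample, coach effect in one arm | 84.6% | 86.0% |
| Large-sample, both effects in both arms | 80.9% | 82.4% |
| Satterthwaite, 5 coaches | 78.6–78.8% | 80.1–80.2% |

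The Satterthwaite ranges cover a coach cluster size of 35 and of n/5.

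**The case against.** The strongest reply accepts the arithmetic and disputes its weight.

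- **400 is not affected.** Both large-sample methods keep power above 80% at 170 per arm, enrolment is given as 2017–2021, and a report would show the observed number. This stands, and it is why the point concerns the justification and not the design.
- **354 is most naturally the number to randomise.** That reading fits the opening sentence, the loss of 53 and the one-arm coach clustering of the model. It is a fair reading and may be what was meant. But the paragraph then attaches 80% power to 177 completers per arm, which fits the other role and is met exactly by a recognised method. Only the sponsor can settle it.
- **The figure below 80% is fragile.** The documents do not state the Satterthwaite method. With coach size n/k, 170 per arm gives 78.8% with 5 coaches, 80.9% with 6 and 83.2% with 8; the Protocol plans interviews with up to eight coaches. Dropping the provider design effect gives 81.0% with 5 coaches. If 14.2 is the SD of a single blood pressure reading, adjusting for baseline would also raise power. All this is right, so 79% is a sensitivity figure. Still, 5 coaches and the provider adjustment are the paragraph's own inputs.
- **Record-based blood pressures may lift the number analysed above 340.** That is possible. However, the Protocol derives 177 from a 15% loss, not from retrieved readings.

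None of these replies makes 200 less 15% equal 177, and no other section repairs it.

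**Conclusion.** The paragraph is wrong as written. At 15% loss, 400 randomised leave 340 (170 per arm), which is 14 fewer in total and 7 fewer per arm than stated. The 177 per arm corresponds to an 11.5% loss. The figure 354 has two incompatible roles, and neither leads to 400.

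The effect on power is small. Going from 177 to 170 per arm costs about 1.5 percentage points under each method. Whether 170 per arm lies above 80% (about 85% or 81%) or about 1 point below it (about 79%) depends on a clustering and degrees-of-freedom method that the Protocol does not give. These figures assume the stated SD, ICCs and cluster sizes, and the lowest also assumes exactly five coaches. The attrition error needs no assumption. The recruitment target of 400 is not in question.

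**What to change.** In Protocol 5.6, Study power and sample size:

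1. Replace 177 per arm by 170 per arm (340 in total) as the number expected from 400 randomised at 15% loss. If 177 is kept, state the loss as 11.5%.
2. Give 354 one role, confirmed by the sponsor: either the number to randomise with 15% loss included (about 301 completers, so that 400 carries a margin), or the completers needed (177 per arm, for which about 417 would be randomised at 15% loss).
3. State how the two ICCs were combined, in which arm coach clustering was applied, and which degrees of freedom were used for five coaches.
4. Restate power at 5 mmHg for 170 per arm under that method: about 85%, 81% or 79%, in the order of the table above.

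The cost is Protocol wording. Recruitment and analysis do not change. The stated completer count becomes slightly less favourable and, under one method, stated power falls about 1 point under 80%.

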
**b) Randomization**

Following baseline assessments, a computerized randomization procedure will assign individuals to either the peer health coach intervention or to the usual care + education control group. Randomization of participants will occur in the order of completed enrollment visits. Randomization lists will be constructed in advance by the study biostatistician using variable

length blocks to ensure the groups are not unbalanced at any time. Concealment will be used to prevent the study staff from obtaining information on the sequence of assignment.

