## 5.6 Data Analysis

- Provide sample size determination and analysis (include anticipated rate of screen failures, study discontinuations, lost to follow-up etc.).
- Describe how, where and by whom the data will be analyzed.

### Specific Aim 1

The primary outcomes are changes from baseline to one year in systolic blood pressure. We will test the primary hypothesis that among Veterans with poorly controlled hypertension and at least one other CVD risk, the **Vet-COACH** intervention targeting behavior change and disease self-management will decrease SBP by 4 mmHg compared to a usual care + education control group.

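### The primary hypothesis is a 4 mmHg SBP difference, but the only stated power (80%) is for 5 mmHg, and that 80% fits about 150 analysed per arm rather than the stated 177

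*Protocol*

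**What the plan says.** Protocol 5.6 (Specific Aim 1) states the primary hypothesis that the intervention "will decrease SBP by 4 mmHg compared to a usual care + education control group". SAP section 6 repeats this word for word.

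The protocol's paragraph on study power and sample size uses 5 mmHg. It makes these statements about numbers:

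- "The sample size we project is n= 354 Veterans, which assumes 80% power, 15% attrition, alpha 0.05". The other inputs are a provider ICC of 0.015 with clusters of 5, and a coach ICC of 0.007 with 5 coaches of 35 participants each.
- "We estimate we will lose 15% of the sample (n=53), which would result in a final sample size of N=400(or 200in each arm").
- The 400 will be "reduced to 177 Veterans in the control and 177 Veterans in the intervention group after an estimated 15% loss of participants".
- The paragraph's stated aim for those completers is "to have a power of 80% to detect a difference of 5 mmHg in systolic blood pressure between groups".

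On variability it says only: "The SD of 14.2 mmHg was taken from a recently published review of CV risk factors among Veterans". It does not say whether this is the SD of SBP level, of change, or of the model residual. The primary model includes a term that "is the baseline BP value", so the distinction affects power. The SAP has no power section.

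**The concern.** There are two separate conflicts. First, the written hypothesis and the design effect size differ by 1 mmHg, and no power is given at the hypothesised value. Second, 354 is described both as a total that already allows for 15% attrition and as the number left after attrition from 400.

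The SAP bases its main conclusions on the pre-specified primary hypothesis. A reader faced with a non-significant result would set it against 80% power, and that figure matches neither the 4 mmHg hypothesis nor the planned analysed number. Neither 4 nor 5 mmHg is a decision threshold: the test is of a zero group coefficient, and the SAP commits to confidence intervals. What is at stake is how the result is interpreted, not the validity of the test.

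**Working it through.** **Inputs.** From the sample size paragraph: difference 5 mmHg, SD 14.2, power 80%, attrition 15%, and the ICCs and cluster sizes above. Two-sided 0.05 is from SAP section 6. Coach clustering in the intervention arm only is from the primary model in both documents. It also fits the stated coaches, since 5 × 35 = 175, which is one arm.

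**Reproducing 354**

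- Unclustered: 2 × (1.960 + 0.8416)² × 14.2² / 5² = 126.6 per arm.
- Provider design effect: 1 + 4 × 0.015 = 1.06, both arms.
- Coach design effect: 1 + 34 × 0.007 = 1.238, intervention arm only.
- Multiplied: the intervention arm is 1.06 × 1.238 = 1.312 and the mean over arms is (1.06 + 1.312)/2 = 1.186. Evaluable total 2 × 126.6 × 1.186 = 300.4, and 300.4/0.85 = 353.4, i.e. 354.
- Added: the mean is 1.179, giving 298.6 evaluable and 351.2 enrolled.

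So 354 is the number to enrol, and the 80% belongs to about 150 analysed per arm.

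**Attrition arithmetic**

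- 0.15 × 354 = 53.1, so the stated loss of 53 is taken from 354, leaving 301.
- 0.85 × 400 = 340, not 354.
- 1 − 177/200 = 11.5%, not 15%.

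**Power, 14.2 as residual SD.** Power = Φ(d/SE − 1.96), with SE = 14.2 × √((DE_int + 1.06)/n), DE_int = 1.06 + (n/5 − 1) × 0.007, and n the number analysed per arm.

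| n per arm | SE | Power at 4 mmHg | Power at 5 mmHg | Detectable at 80% |
|---|---|---|---|---|
| 150 | 1.767 | 61.9% | 80.8% | 4.95 |
| 170 | 1.670 | 66.8% | 84.9% | 4.68 |
| 177 | 1.640 | 68.4% | 86.2% | 4.59 |

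With the coach cluster held at 35, the n = 150 row becomes 61.3% and 80.2%.

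**Other readings of the SD, power at 4 mmHg.** The documents give no baseline to 12-month correlation r, so r is assumed and shown as a range. The ICCs are held fixed, which is also an assumption.

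- Level SD, baseline-adjusted, SD = 14.2 × √(1 − r²):

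| r | 170 per arm | 177 per arm |
|---|---|---|
| 0.3 | 70.9% | 72.5% |
| 0.5 | 79.0% | 80.4% |
| 0.6 | 84.9% | 86.2% |
| 0.7 | 91.8% | 92.7% |

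  80% is reached at r = 0.52 (170 per arm) or 0.49 (177 per arm).
- Change SD, baseline-adjusted, SD = 14.2 × √((1 + r)/2), 177 per arm: 85.7% (r = 0.3), 80.4% (0.5), 75.4% (0.7).

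**Sensitivity to the provider factor.** In this trial "a computerized randomization procedure will assign individuals to either the peer health coach intervention" or control, so a provider's patients may fall in both arms. If they split evenly, the provider factor is about 1 − 0.015 = 0.985 rather than 1.06. With 14.2 as residual SD, power at 170 and 177 per arm is then 69.7% and 71.2% at 4 mmHg, and 87.2% and 88.3% at 5 mmHg.

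All figures use a normal approximation. Allowing for the few degrees of freedom from 5 coaches would lower them.

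**The case against.** The strongest counter-argument is that the sample size paragraph never says how the coach design effect was applied. The intervention-arm-only rule is written for the analysis model, not for the sizing. With both design effects in both arms (1.298 added, 1.312 multiplied), 80% power at 5 mmHg needs 164 to 166 analysed per arm, or 387 to 391 enrolled. That is close to 400. Power is then about 81% at 170 per arm and 82 to 83% at 177, so the error might lie mainly in the figure 177.

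This does not displace the finding. The both-arms version does not reproduce 354, the one-arm version does, and 5 coaches of 35 cover a single arm. Even on the both-arms version, 177 is not the number that gives 80%.

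Four further points deserve weight.

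- Power at 4 mmHg depends on how 14.2 is read, so underpowering is not shown. That stands.
- If the finding is right, the protocol understates its power at 5 mmHg. That also stands, though it does nothing for 4 mmHg.
- The SAP substitutes a medical-record BP within 3 months of the exit date when the exit value is missing, so the analysed number could exceed 340. This is fair; 340 is simply what the plan's own 15% loss implies.
- The SAP gives enrolment as 2017 to 2021 and describes randomisation in the past tense, so no sizing decision remains. This is a reason to correct the text rather than the design.

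**Conclusion.** The concern holds and should be fixed. The 4 versus 5 mmHg conflict and the attrition conflict (340 against 354, 11.5% against 15%) can be read directly from the text and need no modelling. On the plan's inputs, with coach clustering in one arm, the 80% at 5 mmHg corresponds to about 150 analysed per arm; at 177 it would be about 86%.

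If 14.2 is the residual SD, the chance of a non-significant result at 177 per arm is about 14% when the true effect is 5 mmHg and about 32% when it is 4 mmHg. That second figure is conditional. Under the level-SD reading, power at 4 mmHg is at least 80% once r is about 0.5, and the documents do not say which reading applies. The test of the group coefficient, its estimate and its confidence interval are unaffected.

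**What to change.** Keep the pre-specified 4 mmHg hypothesis and do not enrol more. In Protocol 5.6 and SAP section 6:

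- Replace the single 80% statement with power at 4 mmHg and at 5 mmHg, plus the detectable difference at 80% power, all at one analysed number (340, or 170 per arm, if 15% of 400 are lost).
- State that 354 is the enrolment figure (about 301 analysed), and stop using it as the count of completers.
- Say whether 14.2 mmHg is the SD of level, change or residual, and what baseline to 12-month correlation is assumed.
- If 5 mmHg is to become the hypothesis, record that as a dated, disclosed change.

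The cost is a few sentences, with no change to enrolment, model or test. The drawback is that the stated power at 4 mmHg may be below 80%: about 67% at 170 per arm if 14.2 is the residual SD, or under 80% if it is the level SD and r is below about 0.52.
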